To measure seasonal IVE against medically attended laboratory-confirmed influenza, by vaccine brand, then by vaccine type (e.g. by antigen preparation strategy, number of virus strains, adjuvant; see section *Exposure*), then by overall influenza vaccination.

Secondary objectives

To estimate IVE (brand-specific, type specific and total, if possible) against laboratory-confirmed influenza by:

- age group (children, young adults and elderly; the age groups will be further defined in the generic study site level SAP)
- influenza virus type (A, B) and/or subtype (A/H1N1, A/H3N2) and lineage (B/Victoria, B/Yamagata)
- severity/level of health care required (primary health care, hospitalisation)
- risk groups / target groups for vaccination, e.g
 - pregnant women
 - healthcare workers
 - any chronic condition (see Annex 1 and Annex 2)
 - specific chronic conditions (see Annex 1 and Annex 2)
- time since vaccination
- time window in the epidemic season (early, middle, end)(see section Study period)
- previous influenza vaccinations (one or preferably more previous seasons)

To estimate IVE (brand-specific, type specific and total, if possible) against non-specific outcomes with public health relevance, e.g.

- suspected or diagnosed influenza requiring medical attention (primary care and/or hospitalisation)

- respiratory infection, pneumonia or other respiratory conditions requiring hospitalisation, intensive unit care, or leading to death other non-specific outcomes such as cardiovascular events or deterioration of chronic conditions

To estimate brand-specific, type specific or total IVE against laboratory confirmed influenza and/or unspecific outcomes across several seasons, considering the local circulation of the strains and clades detected by the virus surveillance systems, if possible

The details of the analyses will be prescribed in the generic study site level SAP, updated annually according to the characteristics and structure of data available at the participating study sites

Methods

Study design

In each participating study site, a cohort study using secondary data from existing databases or health care registers (see section *Cohort of interest*). To reach appropriate sample size for assessing brand-specific VE, the data from individual studies will be pooled.

Study setting

The population-based study setting is defined by each study site, based on the available data.

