The exposure of interest is vaccination with any seasonal influenza vaccine in the season under investigation (index season). For vaccination status ascertainment, it is crucial to know about the date of vaccine administration and the type/brand of the vaccine. .

The sources of information for the vaccination status may include:

- vaccination registry
- health care visit/hospitalisation register with relevant information of the vaccinations
- relevant insurance company register or prescription register showing evidence of pharmacy delivery or reimbursement of influenza vaccine

- *Each study site to describe the precise way of vaccination status ascertainment.*

Definition of vaccination status

An individual aged ≥ 9 years, or a child aged <9 who has been fully vaccinated before the current season (at least two injectable doses or one LAIV dose) will be considered as

- **vaccinated** with the influenza vaccine of interest (defined exposure) if >14 days have elapsed since the first record of influenza vaccination during the season (see section *Vaccination status ascertainment*)
- **partially vaccinated** during the first 14 days after the first record of vaccination (defined exposure) during the season
- **unvaccinated** until the first vaccination record during the season

A child aged <9 years who has not been fully vaccinated (see above) before the current season will be considered as

- **vaccinated** with the influenza vaccine of interest if >14 days have elapsed since the second record of injectable vaccination or the first record of LAIV vaccination during the current season (see section *Vaccination status ascertainment*)
- **partially vaccinated**
 - during the first 14 days after the second record of injectable vaccination or the first record of LAIV vaccination during the current season
 - after the first record of injectable vaccination until >14 days have elapsed since the second record of vaccination during the current season
- **unvaccinated** until the first vaccination record during the season

If vaccination cannot be assessed as a time-dependent event, and for the description of demographics and baseline characteristics, the vaccination status (yes/no) will be assessed at the end of the individual follow-up.

If the individual has a record of vaccination with a type or brand other than the one of interest (defined exposure) during the study period, she/he will be right-censored at this time point (see section Individual follow-up).

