Potential confounders and effect modifiers

The following list presents known and potential confounders and effect modifiers in population-based IVE studies using secondary data from pre-existing databases (please also refer to DRIVE deliverable 4.1: Framework for analysis of influenza vaccine effectiveness studies).

The minimum set for a pooled analysis is marked with an asterisk (*). If available, also as many as possible of the other determinants will be harmonised between the study sites for pooled analysis according to the guidelines for harmonisation, developed according to availability of data and included in the generic study site level SAP.

- Age*
- Sex*
- Number of healthcare visits 12 months prior to the study period describing a study subject's healthcare seeking behaviour
 - (For children) Also adherence to the local childhood vaccination programme
- Chronic underlying conditions like chronic pulmonary disease, cardiovascular disease, metabolic disorders, renal disease, treatment-induced immunosuppression and disease-induced immunosuppression, medically attended obesity etc.

- (For children) Perinatal and congenital risk factors (e.g. birth weight and/or maturity at birth, perinatal factors, inborn errors of metabolism, relevant malformations and congenital syndromes)
- Number of hospitalisations 12 months prior to the study period to be used as proxy for the severity of the chronic conditions
- Pregnancy
- Influenza vaccination in previous influenza seasons; preferably more than one season,
- Pneumococcal vaccination
- Institutionalization, nursing home residence
- Contraindication to influenza vaccination
- Use of influenza antivirals
- Use of statins
- Socio-economic status or applicable proxy
- Smoking behaviour or parental smoking behaviour (for subjects ≤18 years)
- (For children) Number of siblings

➤ *Each study site to describe the factors included in the study & how these are identified.*

The list will be updated based on results of DRIVE D2.2: Systematic review of the sources of confounding, bias and strategies to manage their impact in influenza vaccine effectiveness studies, due June 2018.

Sources of information

The studies will utilize secondary data from existing population-based national, local or cohort based databases, health and social registers and/or surveillance systems by combining the information with an individual identification number, or relevant aggregation. . Examples of source databases:

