Thus, each study subject may contribute to the follow-up time (person time) as unvaccinated, as partly vaccinated and as vaccinated, according to the definitions in section Exposure, Definition of vaccination status.

Disease episode

Repeated influenza infections during a season are extremely rare, and the first influenza infection affects the probability of the second one. Thus, for specific outcomes, only the first record is considered. However, in addition to the date of the laboratory test for positive influenza finding, the outcome date may be defined as a few days before the test as a proxy for the symptom onset, e.g. for sensitivity analysis.

Instead, there may be repeated visits because of reasons compatible with the non-specific outcomes, e.g. primary care visits before hospitalisation. Outcome-specific definitions for a disease episode will be needed to define the vaccination status at the time of the onset of the disease episode and to indicate which outcome measures are considered to belong to the same disease episode. Outcome-specific definitions for a disease episode are included in the generic site-specific statistical analysis plan (SAP) (Annex 2), to allow harmonization between the individual site-specific analysis plans.

Demographics and baseline characteristics

The baseline characteristics of the study cohort will be described and tabulated by exposure status at the end of the individual follow-up. The association between the baseline characteristics and the exposure status will be investigated using the Fisher's exact test (in case of nominal variables for the baseline characteristics), Mann-Whitney test (in case of ordinal or non-normal continuous variables) or Student's t-test (in case of normal variables). The description of the baseline characteristics will be stratified by the vaccination status at the end of the follow-up and by most important outcome(s) (e.g. laboratory confirmed influenza cases versus others). The proportion of positive influenza tests of all obtained tests will be described, if available.

Measure of effect

The crude (or unadjusted) brand-specific IVE will be estimated as

$$VE = (1 - RR) \times 100\%,$$

where RR denotes the relative risk (ratio of probabilities) or rate ratio (ratio of incidence or hazard rates) of the outcome n for vaccinated individuals versus unvaccinated individuals. The 95% confidence intervals will be calculated as well.

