The analysis must be conducted for each exposure and outcome of interest separately. Confounder-adjusted brand-specific, type specific or overall IVE estimates will be obtained from multivariable regression models, regressing the health outcomes of interest on exposure status, age, sex and the confounders of interest. In case of effect modifiers, an interaction term between exposure and the effect modifier will be included in the regression model or stratified regression analyses will be performed.

Depending on the type of data available, the analytical method(s) will be described in the generic study site level SAP and in a study-specific SAP before the start of the study period. For the outcome of interest, irrespective of its type, multivariable logistic regression will be used, if only the number of events as vaccinated and unvaccinated by number of subjects vaccinated and unvaccinated at the end of the follow-up is known. If the number of events by person time and vaccination status can be assessed, Poisson regression will be used. In case of time-to-event data, Cox regression (proportional hazards) will be used.

Missing data

The cohort should be defined so that the missing data is minimised: the cohort should cover all subjects targeted, especially for the vaccination, and only those subjects. Especially the outcome should be caught non-differentially, i.e. similarly for vaccinated and unvaccinated (see section Study population and follow-up; Cohort of interest). Missing data for events occurring during the follow-up is not available, since 'no record' means by definition 'no event' (unless also the negative

outcome information, e.g. negative influenza tests are available, when a nested case control analysis could be performed).

Missing data may be present, if historical data for background factors at start of the follow-up is not available, e.g. if the subject has moved into the attachment area of the database recently, or it is incomplete, e.g. only part of the databases used in defining the different background factors are available. This subcohort may be excluded from the adjusted analyses.

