Annex 1: The dataset

Annex 1 defines the data elements to be used for estimating brand-specific VE in a population based cohort study using secondary data from pre-existing databases. The minimum dataset is marked with an asterisk(*), but preferably the most important covariates to adjust for will be included. According to these data elements, the analysis database will be developed to include the defined outcome events by person months vaccinated, (partially vaccinated) and unvaccinated, considering the events leading to right-censoring, and the covariates needed for adjustment or stratification.

The database may alternatively be structured for aggregated data, initially based on these data elements.

Instructions for harmonisation of the variables and the structure of analysis database will be provided in the generic study site level Statistical Analysis Plan (SAP), Annex 2. Season-specific updates in Annex 2 will be implemented to Annex 1, if needed.

DRIVE – The dataset for estimating VE in a population based cohort study using secondary data from pre-existing databases. The minimum data set is marked with an asterisk(*)�.

	Variable	Description	Format	Values and coding	Example
General	idcountry*	Country code defined in ISO 3166-1 alpha-2	2 letters text		Finland
	id*	Patient or aggregate identification number	Unique integer		12345678
	cohort*	Cohort name	Text		THL
	region*	Region name	Text		Pirkanmaa
	dataset*	Data set name	text		Elderly
	sex*	Sex	Numeric (Binary)	0=Female 1=Male	0
	dob* (alternatively age)	Date of birth or age at the start of the follow-up (children: months; adults:years)	dd/mm/yyyy	Date between the date of birth of the oldest and youngest study subject	01/01/1960

The follow-up	startdate*	Date of the start of the study period	dd/mm/yyyy	Date within the study period	30/12/2017
	enddate*	Date of the end of the study period ^a	dd/mm/yyyy	Date within the study period	30/12/2017
	middledate	Date separating the early and the middle epidemic season	dd/mm/yyyy	Date within the study period	30/12/2017
	latedate	Date separating the middle and the end epidemic season	dd/mm/yyyy	Date within the study period	30/12/2017
	death*	Died during the follow-up	Numeric (Binary)	0=No 1=Yes	1
	deathdate*	Date of death ^a	dd/mm/yyyy	Date within the study period	30/12/2017
	moved(*)	Moved out of the cohort catchment area during the follow-up	Numeric (Binary)	0=No 1=Yes	1

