	movedate(*)	date of moving out of the catchment area of the cohort ^a	dd/mm/yyyy	Date within the study period	30/12/2017
	Outcome/ right-censoring dates	infl*	Any positive influenza test during the follow-up	Numeric (Binary)	0=No 1=Yes
		infldate*	Date of positive influenza test ^b	dd/mm/yyyy	Date within the study period
		inflA*	Any positive influenza A test during the follow-up	Numeric (Binary)	0=No 1=Yes 9999=No information

	inflAdate*	Date of positive influenza A test ^b	dd/mm/yyyy	Date within the study period (no information =99/99/9999)	30/12/2017
	inflH1N1	Any positive influenza A(H1N1) test during the follow-up	Numeric (Binary)	0=No 1=Yes 9999=No information	1
	inflH1N1date	Date of positive influenza A(H1N1) test ^b	dd/mm/yyyy	Date within the study period (no information =99/99/9999)	30/12/2017
	inflH3N2	Any positive influenza A(H3N2) test during the follow-up	Numeric (Binary)	0=No 1=Yes 9999=No information	1
	inflH3N2date	Date of positive influenza A(H3N2) test ^b	dd/mm/yyyy	Date within the study period (no information =99/99/9999)	30/12/2017
	inflB*	Any positive influenza B test during the follow-up	Numeric (Binary)	0=No 1=Yes 9999=No information	1
	inflBdate*	Date of positive influenza B test ^b	dd/mm/yyyy	Date within the study period (no information =99/99/9999)	30/12/2017
	inflYamagata	Any positive influenza B/Yamagata test during the follow-up	Numeric (Binary)	0=No 1=Yes 9999=No information	1

	inflYamagatadate	Date of positive influenza B/Yamagata test ^b	dd/mm/yyyy	Date within the study period (no information =99/99/9999)	30/12/2017
	inflVictoria	Any positive influenza B/Victoria test during the follow-up	Numeric (Binary)	0=No 1=Yes 9999=No information	1
	inflVictoriadate	Date of positive influenza B/Victoria test ^b	dd/mm/yyyy	Date within the study period (no information =99/99/9999)	30/12/2017
	outcomeXdate	Date of defined time of outcome X ^c	dd/mm/yyyy	Date within the study period	30/12/2017
Exposure/ right-censoring dates	inflvac	Vaccination at least once with any influenza vaccine during the follow-up	Numeric (Binary)	0=No 1=Yes	1
	inflvacdate*	First date of any influenza vaccination ^d	dd/mm/yyyy	Date within the study period	30/12/2017
	inflvac2	Vaccinated twice with any influenza vaccine during the follow-up	Numeric (Binary)	0=No 1=Yes	1
	inflvacdate2	Second date of any influenza vaccination ^e	dd/mm/yyyy	Date within the study period	30/12/2017

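### Vaccine effectiveness by time since vaccination has no fitted analysis: stratifying leaves no unvaccinated comparator, and the stated Poisson model has no calendar-time term.

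*Combined protocol and SAP*

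**What the plan says.** Secondary objectives lists "time since vaccination" among the factors by which effectiveness against laboratory-confirmed influenza is to be estimated, where possible.

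Measure of effect defines effectiveness through a relative risk or rate ratio "for vaccinated individuals versus unvaccinated individuals". For effect modifiers it says that "an interaction term between exposure and the effect modifier will be included in the regression model or stratified regression analyses will be performed". It then assigns the model by data type:
- logistic regression where only counts by vaccination status at the end of follow-up are known;
- Poisson regression where events by person-time and vaccination status are known;
- Cox regression for time-to-event data.

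Under Definition of vaccination status, a person is unvaccinated "until the first vaccination record during the season". Under Individual follow-up, follow-up starts at a fixed date and "each study subject may contribute to the follow-up time (person time) as unvaccinated, as partly vaccinated and as vaccinated".

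Annex 1 says that "the analysis database will be developed to include the defined outcome events by person months vaccinated, (partially vaccinated) and unvaccinated", together with censoring events and whatever covariates adjustment or stratification requires. Its minimum dataset includes "First date of any influenza vaccination".

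No section gives bands, a reference group or a time scale for time since vaccination. Details are left to the generic site-level SAP (Annex 2), which is still a placeholder.

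**The concern.** Time since vaccination differs from the other listed factors because it exists only in the vaccinated. A site that applies the general rule as written meets an empty comparator if it stratifies, and a redundant column if it fits the usual main effects plus product. It must then choose its own way out.

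The easiest choice with person-time data is to compare each band of vaccinated time with all unvaccinated time in a Poisson model. Vaccination is concentrated in autumn, so each band covers a particular part of the season, while the unvaccinated reference covers all of it. Calendar time appears neither in the Poisson rule nor in the list under Potential confounders and effect modifiers. The result can be false waning or false strengthening, and site estimates with different epidemic timing would then be pooled.

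**Working it through.** The plan gives no figure for this objective, so there is none to reproduce. The check covers identifiability and then bias.

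**1. Stratified regression.** In any stratum of time since vaccination, unvaccinated person-time is 0 by definition. No ratio exists.

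**2. Interaction.** Let V be vaccinated (0/1) and T time since vaccination, with T = 0 in the unvaccinated.
- Columns 1, V, T, V×T: T equals V×T, so the rank is 3 of 4. With four bands the full factorial has 8 columns and rank 5.
- The contrast for effectiveness at time t is (1, 1, t, t) − (1, 0, 0, 0) = (0, 1, t, t). It is a difference of two rows of the design, so it is estimable despite the redundancy.
- Dropping the T main effect leaves 1, V, V×T. With four bands this is rank 5 of 5, and it gives the same fit as treating the bands as exposure levels.

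**3. Bias without calendar time, constant effectiveness.** Assumptions, none from the plan except the 5% attack rate and 50% coverage, which are planning values in Annex 3:
- 224 days of follow-up, and a bell-shaped daily hazard h(d) scaled to a 5% attack rate in the unvaccinated;
- uniform uptake to 50% coverage in weeks 2–9;
- true effectiveness 50% from day 15 after vaccination.

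Crude band estimate = 1 − (band events / band person-days) ÷ (unvaccinated events / unvaccinated person-days). Aligned estimate = 1 − band events ÷ Σ over days [band person-days(d) × unvaccinated risk(d)]. These are expected values, without sampling error. Weeks 2–9 can be read in two ways, so both are shown.

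| Uptake days | Epidemic peak (SD) | 15–60 d | 61–120 d | 121–180 d | All time >14 d |
|---|---|---|---|---|---|
| 7–62 | day 110 (18) | 24% | −51% | 93% | 26% |
| 7–62 | day 125 (21) | 63% | −60% | 70% | 26% |
| 14–62 | day 110 (18) | 12% | −48% | 96% | 23% |
| 14–62 | day 125 (21) | 58% | −66% | 78% | 23% |
| any, aligned by day | either | 50% | 50% | 50% | – |

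The reason shows in the dates. With uptake on days 7–62, the 61–120 day band spans calendar days 7 + 61 = 68 to 62 + 120 = 182, across the peak. The 121–180 day band starts at 7 + 121 = 128, one SD after a peak on day 110. The unvaccinated reference also includes the quiet weeks at either end.

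**4. Bias with true waning.** A simulated cohort of 400,000 had 50% coverage, vaccination over weeks 0–11 of 33, a peak at week 17 (SD 5 weeks) and a 5% attack rate. Bands were weeks 3–8, 9–16, 17–24 and 25+ after vaccination.

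| | Band 1 | Band 2 | Band 3 | Band 4 |
|---|---|---|---|---|
| Truth | 60% | 50% | 40% | 30% |
| Poisson, no calendar term | 36% | −17% | 43% | 88% |
| Poisson, calendar week | 58.9% | 48.1% | 40.7% | 27.1% |
| 95% CI (calendar week) | 56.0–61.5 | 45.7–50.4 | 36.7–44.5 | 9.5–41.3 |
| Events | 1014 | 2467 | 1119 | 96 |

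Without the calendar term, steady waning appears as strengthening from the second band on. With it, the truth is recovered.

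**The case against.** The strongest defence has four parts.

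- **The interaction option can work.** A reader might infer from the rank deficiency that effectiveness by time since vaccination cannot be estimated under the rule. Step 2 shows otherwise: the contrast is estimable, and the plan asks for an interaction term without requiring a main effect of the modifier. This part stands.
- **The rule is never tied to this objective.** The section introduced by "The following list presents known and potential confounders and effect modifiers in population-based IVE studies" does not include time since vaccination, and the effect-modifier sentence is conditional. That is correct, but the objective is then left with no stated analysis.
- **The ingredients are present and the detail is deferred.** Vaccination dates, time-dependent status and Cox regression are all in the plan. With a fixed common start, time on study within a site is calendar time, so Cox risk sets are already aligned. A reader might also infer that the Annex 1 database cannot hold the bands. The text does not support that, because the same sentence admits covariates for adjustment or stratification and the structure is left to Annex 2. All this stands, but Annex 2 has no content yet and the Poisson route remains without a time term.
- **The bias is not caused by the interaction rule.** This also stands. In step 3 the same crude comparison lowers even unbanded effectiveness from 50% to 23–26%. The source is missing calendar-time control, and banding makes its effect much larger. The early, middle and late season periods under Study period could give coarse control, but the plan does not link them to the Poisson model or to this objective.

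**Conclusion.** The concern holds in a limited form. For one secondary objective, the general effect-modifier rule does not fit if read literally: its stratified branch has no comparator, and its interaction branch needs nesting that the plan does not state. The Poisson model as written has no calendar-time term and can give band estimates wrong by tens of percentage points and wrong in sign: about −60% to above 90% when the truth is 50% throughout.

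Those sizes rest on assumed epidemic curves and uptake, and they move by up to about 12 points with the exact uptake dates. The direction of error in a given band depends on when the epidemic peaks. They apply to the Poisson route without calendar control, not to Cox regression from the common start date. Sites with only end-of-follow-up counts cannot contribute to this objective under any model.

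It would go too far to say that the plan has no workable analysis. A sound one is within reach of the data it collects; it has not been specified.

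**What to change.** In Measure of effect, or in Annex 2 when it is written:
- analyse time since vaccination as a time-varying exposure with levels unvaccinated, partially vaccinated, and vaccinated in predefined bands of days, with unvaccinated person-time as the common reference;
- use calendar time as the Cox time scale, or calendar week or month as a covariate in Poisson regression;
- add a test for trend across the vaccinated bands;
- limit the objective to sites with dated vaccination.

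In Annex 1, split all person-months by calendar period, and vaccinated person-months by the same bands.

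The cost is wording and an additional split of person-time from dates already in the minimum dataset. The statistical price is fewer events per band. Scaling the step 4 events to the recommended 5000 subjects (a factor of 400,000 / 5000 = 80) gives about 13, 31, 14 and 1 events in the four bands. Intervals from a single site of that size would be wide, so the bands should be few and chosen with the pooled analysis in mind.
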